8.4.2 Appropriate to Use

Non-selectors will be classified on the variable Appropriate for Use as follows:

Yes: meets the label criteria for use, representing those who could have selected appropriately, but did not (**Cell C**).

No: does not meet the label requirements for use, and appropriately did not select (**Cell D**). This includes those subjects who otherwise might have met the strict criteria for appropriate use according to the DFL, but who give a medically appropriate rationale for their non-selection decision. For example, if a subject who otherwise meets the labeled criteria for use does not select the product and for example cites the desire to use another EC product so they can restart hormonal contraception immediately as their reason for not selecting, that subject will be re-classified from Cell C to Cell D. A physician will review the casebook for each subject who falls into Cell C to determine if any subjects meet that criterion.

Selectors will be classified on the variable Appropriate for Use as follows:

Yes: either meets the strict label criteria for use (1-Correct Selectors) or reported and measured characteristics justify the selection decision (2-Acceptable Selectors), representing those who chose to use the product who made a clinically acceptable decision despite not meeting the strict label criteria for use (**Cell A**).

No: does not meet strict label criteria and reported and measured characteristics do not justify the selection decision (3-Incorrect Selectors), representing those who chose to use the product, but should not have (**Cell B**).

Complete definitions of Correct, Acceptable, and Incorrect Selectors follow:

- 1) Correct Selectors. Subject meets the strict criteria of the Drug Facts label, including:
 - a) No contraindications (not pregnant or breastfeeding, no known allergy to any of the ingredients, no previous use of ella® within the same menstrual cycle, no use as regular birth control)
 - b) Is a woman of childbearing potential. This would include all women who do not report any of the following: surgical sterilization (tubal ligation, hysterectomy, or bilateral oophorectomy) or postmenopausal for at least one year
 - c) Has had unprotected sex in the 5 days prior to use of the product
- 2) Acceptable Selectors. Subject does not meet the strict criteria of the DFL, but selection is classified as appropriate because they are judged clinically (see Section 8.4.3) to be an appropriate selector. This group is expected to be quite small.
- 3) Incorrect Selectors. This group includes selectors who are not correct or acceptable, including having any of the following:
 - a) A contraindication to the product (are pregnant or breastfeeding, or has an allergy to one of the ingredients, previously used ella® within the same menstrual cycle, or use as regular birth control)
 - b) Is a man
 - c) Is a woman without childbearing potential. This would include all women who report any of the following: surgical sterilization (tubal ligation, hysterectomy, or bilateral oophorectomy) or postmenopausal for at least one year
 - d) Has not had unprotected sex in the 5 days prior to use of the product

Please note, for the purposes of this study, for all subjects who qualify to purchase the product, self-selection will be evaluated at the time of use, rather than time of purchase, and each instance of use will be independently evaluated for the self-selection endpoints. For example, if a subject purchases two packages of the study product, using one immediately and one four weeks later, each of those use instances will be evaluated for appropriateness. Because the timing of the most recent episode of unprotected sex is one of the elements of appropriate use, behavior surrounding each dosing instance must be the basis for self-selection evaluation.

Subjects who are either pregnant or breastfeeding and who select the product will be precluded from purchasing, and will be classified as incorrect selectors.

8.4.3 Physician Mitigation

Subjects occasionally make a decision to select a product for use that according to the strict DFL-defined algorithm appears to be an incorrect decision, but, when examined clinically, is acceptable. This review and clinical judgement will be done by three physicians working independently, evaluating the entire casebook for each Incorrect Selector (as defined above in Section 8.4.2) for evidence that the subject made a clinically justifiable selection decision. Their assessments are then compared, and any discrepancies resolved by a majority rule.

Each physician reviewer will review the entire casebook for every subject who falls into Cells B or C of the self-selection table. For subjects in Cell B, physicians will make an assessment of whether the use instance was acceptable based on clinical judgement of the subject's behavior and her stated reasons for those actions. If yes, each physician's complete rationale for mitigation will be recorded and the subject will be reclassified from Cell B to Cell A. For subjects in Cell C, physicians will make an assessment of whether the non-selection decision was based on a reasonable medical rationale. If yes, each physician's complete rationale for mitigation will be recorded and the subject will be reclassified from Cell C to Cell D.

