Subjects also will be provided with a self-administered urine pregnancy test and given instructions to use the test at the end of the study period. Results will be recorded in the database in the End-of-Study interview.

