5.3.2.3 End-of-Study Interview

In most cases, the EOS interview will take place in conjunction with the 6-week telephone call together with the week 6 interview. However, it is conceptualized as a separate interview in order to allow for collection of key end of study measures in cases where subjects elect to withdraw before the 6-week telephone call. The end-of-study interview will collect information from the subject regarding the use of other forms of contraception, including other uses of EC (if any) within the study period, and the timing of such use. Subjects will also be asked about possible pregnancy, and will be asked to report the results of their EOS pregnancy test. This interview allows for direct questions about the rationale behind any behaviors that are not consistent with the DFL and CIL, without concern about biasing the subject's subsequent behavior.

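### For Cell B subjects who used the product, Section 8.4.3 lets the mitigating physicians see outcomes after the dose that are not part of the stated criterion, and their rulings can only raise Endpoint E

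*Protocol*

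**What the plan says.** Section 8.4.3 states the review material twice: "This review and clinical judgement will be done by three physicians working independently, evaluating the entire casebook for each Incorrect Selector", and then "Each physician reviewer will review the entire casebook for every subject who falls into Cells B or C of the self-selection table". Nothing is withheld.

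For Cell B the criterion is that "physicians will make an assessment of whether the use instance was acceptable based on clinical judgement of the subject's behavior and her stated reasons". If the answer is yes, "the subject will be reclassified from Cell B to Cell A". For Cell C the question is whether non-selection had a reasonable medical rationale, and if so "the subject will be reclassified from Cell C to Cell D". Each physician's rationale for mitigation is recorded, and disagreements go to the majority.

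The study record also contains later outcomes. In the end-of-study interview (Section 5.3.2.3) subjects "will be asked to report the results of their EOS pregnancy test", and Section 5.2.2 says "Results will be recorded in the database in the End-of-Study interview". Section 7.12.2 puts adverse events on the CRF.

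**The concern.** The physicians are asked whether a use decision was clinically justifiable. A reviewer who already knows that a late or repeat dose was followed by no pregnancy and no adverse event may find it easier to call that dose acceptable. A reviewer who sees a pregnancy may find it harder. Either way the judgement is affected by something outside the stated criterion.

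The protocol guards against this on the other axis of the 2x2 table. Section 8.4.1 says that, for most subjects, information offered after the selection phase does not count when classifying selectors and non-selectors. The more subjective judgement, appropriateness of use, has no comparable limit.

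At stake is the credibility of Endpoint E (correct selection) and of D/(B+D), which Section 9.3.3.2.2 calls the typical self-selection metric. Once reviewers have seen the outcomes, its influence on their rulings cannot be removed afterwards.

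**Working it through.** **1. Are later outcomes in the material?** Section 8.4.3 does not define the casebook. The pregnancy result is in the database and adverse events are on the CRF, so for a user with follow-up an entire casebook would contain both. This is an inference, but a short one. The end-of-study interview also collects the subject's reasons for departing from the label together with her pregnancy result, so a reviewer looking for reasons is led to the outcome.

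**2. Who is exposed?** Section 3.3.2 bars pregnant, breastfeeding, male and allergic subjects from the use phase, so those selectors have no outcome after a dose. Cell C non-selectors do not take the product. The exposed group is Cell B users: for example, no unprotected sex in the 5 days before the dose, repeat use in the same cycle, use as regular birth control, or no childbearing potential.

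**3. Direction of the rule.** Section 9.3.3.2.2 gives E = (A + D)/(A + B + C + D) = (A + D)/N. Moving one case from B to A gives (A + 1 + D)/N, an increase of 1/N. The other metric goes from D/(B + D) to D/(B − 1 + D), also an increase. No ruling can lower either one.

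**4. Size per case.** The planning figure in Section 9.1 reproduces: 950/0.75 = 1267, stated as up to 1270 interviewed. Not all of these need reach a scored decision, so 1270 is a ceiling for N.
- N = 1270: 1/1270 = 0.08 points per case.
- N = 650 (assumed): 1/650 = 0.15 points per case.

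**5. Illustration with assumed counts.** Take B = 40, D = 10, and an acceptance rate that rises from 30% to 45% when outcomes are seen.
- Cases moved: 40 × 0.30 = 12 against 40 × 0.45 = 18, so 6 extra.
- E: +6/650 = 0.9 points, or +6/1270 = 0.5 points.
- D/(B + D): 10/(28 + 10) = 26% against 10/(22 + 10) = 31%.

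**6. Net direction of hindsight.** Let b be the share of scored decisions that are exposed Cell B cases and q the share of those with a bad outcome. Let u be the rise in acceptance after a good outcome and d the fall after a bad one. The shift in E is b × [(1 − q)u − qd], which turns negative when q exceeds u/(u + d). All values below are assumed.

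| q | u | d | Net change in acceptance | Shift in E, b = 5% | Shift in E, b = 10% | Break-even q |
|---|---|---|---|---|---|---|
| 0.02 | 0.10 | 0.10 | 0.096 | 0.48 points | 0.96 points | 0.50 |
| 0.10 | 0.10 | 0.30 | 0.060 | 0.30 points | 0.60 points | 0.25 |
| 0.02 | 0.20 | 0.50 | 0.186 | 0.93 points | 1.86 points | 0.29 |

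The net effect is upward unless bad outcomes reach roughly a quarter to a half of the exposed cases. The protocol expects very few inappropriate subjects, so these values of b are generous.

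**7. The whole mitigation step, for scale.** With N = 1270 and B + C at 5% (assumed), E is 1206/1270 = 95.0% before mitigation and 1238/1270 = 97.5% if half the cases are mitigated. This is the effect of mitigation itself, not of hindsight. It shows why both values are worth seeing.

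**The case against.** The strongest reply is that later information can be legitimate evidence. Section 8.4.2 evaluates selection at each use, and not being pregnant is a criterion at that time. The enrollment test covers Day 1 only, so for a later dose a positive result may show that the subject was already pregnant. An adverse event can matter too: the leaflet (Section 18.2) tells a user who vomits within 3 hours to ask a professional about repeating the dose, and that bears on a repeat use in one cycle. A reader might infer that no later outcome is relevant to the judgement. The documents do not support that, and the fix has to allow for it.

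A cut-off at the moment of use would also fail, because timing and behavior are collected only in the later interviews (Sections 5.3.2.1 to 5.3.2.3).

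The existing safeguards have some value. Independent review and majority rule reduce individual error, and recorded rationales can be audited. They do not remove a tendency shared by three physicians who see the same outcome, and a rationale need not reveal what prompted it.

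The contents of the casebook and a display with and without mitigation may be settled in the SAP, which is not shown. But the instruction to use the entire casebook is stated in the protocol. It is not a detail left open.

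**Conclusion.** The point holds for Cell B users only. The protocol gives reviewers outcomes that its own criterion does not call for, and every reclassification raises Endpoint E. The net effect is probably favourable. Its size is unknown and likely small: 0.08 points per case at N = 1270, and under 2 points in total even under the generous assumptions above. The documents give no count for Cell B, no mitigation rate and no measure of hindsight.

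Two stronger readings should be resisted.
- A reader might infer from the leaflet's figure of 98 in 100 women not becoming pregnant that nearly every casebook will look benign and the bias is certainly upward. That figure applies to use as directed, and Cell B users fall outside the strict label criteria. What is certain is that the reclassification rule works in one direction. Hindsight itself can work in either.
- A reader might infer that a study conclusion is at risk. The 90% threshold in Section 9.3.2 applies to primary endpoints A to C, whose definitions in Section 9.3.1 do not use mitigation. Endpoint E is secondary and has no stated threshold.

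This is an inexpensive improvement to a secondary endpoint, not a flaw in the primary analysis.

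**What to change.** In Section 8.4.3, for Cell B subjects who used the product, replace the instruction to review the entire casebook with:

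> Reviewers receive all casebook data on the use instance under review, whenever collected: timing, behavior, stated reasons, medical history, the criterion that led to the Cell B classification, and events before that dose. The end-of-study pregnancy result, pregnancy outcomes and adverse events arising after that dose are withheld until each physician's assessment and rationale are recorded, except where they are themselves the basis for the Cell B classification (for example, evidence that the subject was already pregnant at that dose).

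Tying the limit to the dose under review also covers subjects with more than one dose: vomiting after a first dose stays visible when the second is judged. Also report Endpoint E before and after mitigation.

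The cost is a redacted listing, prepared by the CRO, for a small number of Cell B users. Cell C casebooks and those of selectors barred from the use phase need no redaction.

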8.4.4 Coding of Open-ended Responses

The responses to open-ended questions will be coded to make them amenable to numeric analysis and display. Coding procedures will follow PEGUS Research SOP DAT:008. Once data for at least 50% of subjects has been collected, listings of individual responses for each question will be created. The listings will be reviewed to discover the underlying conceptual structure suggested by the data, and a coding frame (a list of categories, each of which is assigned a one or two-digit number) will be created for each question. The coding frames will be reviewed and revised as necessary when 100% of the data is collected and cleaned. When the coding frame is finalized, reviewed and approved, coding may be performed.

Coding will be done using data from the final, clean data set. Two coders working independently will code each question with a significant number of responses (e.g. >25). Their code assignments will then be compared and the Coding Supervisor will resolve any discrepancies. Multiple codes (typically no more than seven) may be assigned to elements of one response. Once coded, these data will be displayed in standard frequency tables. For these tables, the unit of analysis, and thus the denominator, changes to become the number of responses rather than the number of subjects.

9 DATA ANALYSIS/STATISTICAL METHODS

A detailed methodology for the statistical analyses of the data collected in this study will be documented in a Statistical Analysis Plan (SAP), which will be finalized prior to database lock. The SAP may modify the plans outlined in the protocol; however, any major modifications to the primary endpoint definition and/or its analysis will also be reflected in a protocol amendment.

This is a naturalistic, observational trial to assess use patterns from the prospective OTC population in a simulated OTC setting. The analyses will largely employ descriptive statistics including frequencies, percentages and appropriate summary statistics.

9.1 Sample Size Determination

For the purposes of this AUT, sample size has been set for practical and logistical reasons at approximately 950 purchasers. Given that subjects are recruited after independently seeking EC, most of those who enter the self-selection phase are expected to purchase, and most purchasers are expected to actually use the product during the study. If approximately 75% of subjects pass the screening criteria, self-select

and both qualify and agree to purchase and enter the use phase, it is expected that up to 1270 subjects will need to be interviewed to yield 950 purchasers.

Assuming approximately 950 purchasers, if 80% of those purchasers use the product within the study period, that would yield a user population of 760. Estimating approximately 40% of users will have had recent hormonal contraceptive use would yield a recent hormonal contraceptive users population of 305. Allowing for a further 20% loss to follow-up yields a user population of approximately 608 and a recent hormonal contraceptive user population of 245.

Because actual use trials are not hypothesis-testing comparative trials, study sample size is designed to allow for adequate evaluation of key endpoints across all subjects and among several subgroups. As the analysis of actual use trials typically focuses on estimating the proportion (and associated 95% confidence intervals) of individual endpoints, sample size is most often based on the number of subjects needed to constrain the confidence interval (CI) to a limited range. For this study, assuming 85% correct response (the confidence interval depends on the actual point estimate), a sample of 608 subjects would constrain the CI to $\pm 3.1\%$. For purposes of illustration, Table 5 provides the 2-sided exact 95% confidence interval for various sample sizes around a point estimate of 85%.

Table 5 Two-sided 95% CIs for Various Sample Sizes Around 85% Point Estimate

	N=760 ^a	N=608 ^b	N=245 ^c	N=143 ^d
95% CI around a point estimate of 85%	$\pm 2.7\%$	$\pm 3.1\%$	$\pm 5.1\%$	$\pm 7.0\%$

^a User population (maximum)

^b User population (allowing for loss-to-follow up)

^c Recent hormonal contraceptive users

^d Low literacy subjects

9.2 Analysis Populations

The populations of interests are defined as follows:

- Responder Population: Subjects who accept the invitation to participate and begin the screening process (including those who do not meet screening criteria for proceeding to the self-selection phase).
- Self-Selection Population: Subjects who accept the invitation to participate and meet study inclusion criteria, participate in a face-to-face interview at the study site and make a self-selection and purchase decision.
- Purchasers: Subjects who meet study enrollment criteria and purchase the study medication.
- User Population: Subjects who take at least one dose of study medication during the study.
- Recent hormonal contraceptive users: Subjects in the user population who also report recent hormonal contraceptive use (i.e., use of a hormonal contraceptive within the previous two months).

9.3 Endpoint Analysis

A summary of the disposition of subjects (including responders, self-selection population, purchasers and users) and reasons for exclusion from these populations will be provided. Demographic characteristics, medical history and other background information will be summarized for the responder, self-selection, purchaser, and user populations.

Frequencies and percentages will be presented for categorical data, mean, standard deviation (SD); median, and range will be presented for numerical data.

Frequencies, percentages and 2-sided 95% CI will be calculated for the primary and secondary endpoints using the exact method. For the primary endpoints, it will be concluded that the established target threshold is reached if the lower limit of the CI of the point estimate is equal to or exceeds the value of the pre-determined threshold.

Several of the endpoints are based on dosing instance, rather than by subject, as subjects have the potential to take more than one dose over the course of the study. Correctness of selection or behavior can only be evaluated at the time of use, rather than at the time of purchase. However, for each of those endpoints a secondary analysis by subject will also be presented.

Endpoints and demographics will be presented for subgroups of interest, with subjects dichotomized on the corresponding variables, which include (but are not necessarily limited to) literacy, gender, age (adolescent vs. adult women), and history of HBC use.

A more detailed description of planned data analysis procedures will be found in the SAP which will be approved and signed before the database is locked.

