4.3.2 Preparation and Dispensing

All subjects who use study medication will take ulipristal acetate 30 mg. Subjects are to use the investigational product (IP) based on their understanding of the directions on the outer packaging including DFL and inside the product packaging (in the CIL).

Subjects will be allowed to purchase the study product at the study site. Subjects will not be allowed to purchase more than 9 single-count packages during the entire study period. They will be allowed to purchase up to 3 packages at a time (on any one calendar day) during their first visit to the site and may return to the study site at any time to purchase additional medication, up to a total of 9 packages, during the following 6 weeks. These purchase limits will not be disclosed to subjects unless they try to purchase more than 3 packages in a day or more than 9 packages over the course of the study. Any such requests that exceed the purchase limits will be recorded.

It is typical to allow participants in an actual use trial to purchase more IP than they would use under usual conditions, in order to allow for the observation and measurement of overuse/misuse of the product, should it occur. In this case, as there is no true “typical use” for EC because the product is used under unusual circumstances (in instances of unprotected sex), purchase limits were chosen to allow for reasonable behavior on the part of subjects, even if beyond the label directions, without allowing for larger scale misuse. While the expectation is that the vast majority of subjects will purchase a single package of the IP, it would be reasonable for subjects to purchase additional doses for advance provision. The daily limit was set at three to account for this. Again, while the expectation is that very few subjects will return for resupply, in order to observe overuse or misuse should it occur, repurchase will be allowed. Indeed, given FDA’s expressed concern about the potential for misuse of this product, in previous interactions FDA agreed with the planned purchase limits as these limits would allow the AUT to estimate the likelihood of potential misuse when the product is available OTC.

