9.3.1 Primary Endpoint Analysis

Frequencies, percentages and two-sided exact 95% confidence intervals will be calculated for the three primary endpoints for the entire study population and for selected subgroups.

9.3.1.1 A: Actual Use: Proportion of dosing instances among user population taken within 120 hours (5 days) of most recent episode of unprotected sex.

The first primary endpoint is the proportion in which the denominator includes all dosing instances of the IP and the numerator includes all dosing instances of the IP which were taken within 120 hours (5 days) of the subject's most recent episode of unprotected sex.

9.3.1.2 B: Actual Use: Proportion of dosing instances among user population in which no more than one tablet was taken.

The second primary endpoint is the proportion in which the denominator is all discrete dosing instances of the IP and the numerator includes all dosing instances where no more than one tablet was taken.

9.3.1.3 C: Self-Selection: Proportion of female selectors who are not pregnant at the time of selection decision.

The third primary endpoint is the proportion in which the denominator includes all females who selected to use the product (regardless of whether they purchased/used) and the numerator includes all female selectors who were not pregnant at the time of the selection decision. In the case of subjects that report not being pregnant, sign consent and then receive a positive result on the pregnancy test, the second selection decision will be used for analysis of this endpoint.

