9.3.2 Target Thresholds

The threshold for the three primary endpoints is 90%. The objective will be considered met for these endpoints if the lower bound of the 2-sided 95% CI for each endpoint meets or exceeds the established threshold.

- *A: Actual use: Proportion of dosing instances among user population taken within 120 hours (5 days) of most recent episode of unprotected sex.*

The Sponsor proposes to test this message as a primary endpoint because it communicates directions for effective use of ella®, and the limited time-window for its effective use. Use of ella® after 5 days diminishes or abolishes the product's efficacy, although it is not expected to introduce any drug-related risks. Despite the fact that this label language is almost identical to the label language tested, approved, and in-market for Plan B One-Step (PBOS) (which is "Take as soon as possible and no later than 3 days (72 hours) after unprotected sex"), the Sponsor will test this as a primary endpoint.

Testing it as a primary endpoint would test whether the longer time window (5 vs 3 days) during which consumers may benefit from ella® use is well-followed. This would also allow us to confirm that consumers do not take ella® later after unprotected intercourse than recommended in the product label.

A performance threshold of 90% is proposed because while taking the product within the 5-day window is very important to maximize effectiveness, taking it outside of the 5 days window is not expected to introduce any serious drug-related risks.

- *B: Actual Use: Proportion of dosing instances among user population in which no more than one tablet was taken.*

The Sponsor proposes to test this message as a primary endpoint in the context of FDA's recommendation to demonstrate in an AUT whether consumers misuse ella® and one of the potential misuse scenarios would be the intake of more than the recommended dose, which would be assessed through this endpoint.

A threshold of 90% was designated despite the fact that dose-finding studies using up to 200 mg of UPA (more than 6 times the intended 30 mg dose) demonstrated no safety concerns (HRA2914-503). Accordingly, it is likely that taking more than the recommended dose is likely to impose little or no additional risk in women.

- *C: Self-Selection: Proportion of female selectors who are not pregnant at the time of selection decision.*

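### The lower limit that decides endpoints A and B treats repeat doses from one woman as independent: a low-severity flaw, and of measurable size for endpoint A only

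*Protocol*

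**What the plan says.** All references are to the protocol.

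- **Unit.** Section 9.3: "Several of the endpoints are based on dosing instance, rather than by subject, as subjects have the potential to take more than one dose". For A, in Section 9.3.1, "the denominator includes all dosing instances of the IP". For B the denominator is again the discrete dosing instances, and "the numerator includes all dosing instances where no more than one tablet was taken".
- **Interval.** Section 9.3: "Frequencies, percentages and 2-sided 95% CI will be calculated for the primary and secondary endpoints using the exact method".
- **Decision.** Section 9.3.2: "The objective will be considered met for these endpoints if the lower bound of the 2-sided 95% CI for each endpoint meets or exceeds" the threshold, which is 90%.
- **By-subject result.** Section 9.3: "However, for each of those endpoints a secondary analysis by subject will also be presented". No pass rule is attached to it.
- **Repeat use.** Section 4.3.2: "Subjects will not be allowed to purchase more than 9 single-count packages during the entire study period", with at most three on one calendar day. The same section expects nearly all women to buy one package and few to come back. Section 8.4.2 gives the example of one woman using two packages four weeks apart and evaluates each use separately.

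**The concern.** An exact interval on a pooled count is a binomial interval. It is valid if the instances are independent with a common probability. A woman who takes one dose too late may well take the next one late too, so her instances carry less information than the same number from different women. The planned limit is then too high, and the error favours success.

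The unit, the interval and the pass rule are all fixed in the protocol, so the flaw lies in the decision rule itself and not in a detail deferred to the SAP. What is at stake is a primary verdict close to the pass boundary. A result just above it could be declared a success when a limit that respects the clustering would fall below 90%.

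**Working it through.** **1. Reproduce the plan's precision figures.** Exact lower limit for x successes in n: L = Beta quantile(0.025; x, n − x + 1). At 85%, the distance from the estimate down to L is 2.74, 3.09 and 5.10 points for n = 760, 608 and 245, and 6.98 points for 121/143. Table 5 gives 2.7, 3.1, 5.1 and 7.0. So the exact method is the standard binomial (Clopper-Pearson) interval, and Table 5 counts subjects.

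**2. Baseline.** Section 9.1 gives 950 × 0.8 = 760 users and 760 × 0.8 = 608 after loss to follow-up. If each of 608 women doses once, the lowest passing result is 562/608 (92.43%, L = 90.04%); 561/608 gives 89.85% and fails. P(pass | true 90%) = 2.33%.

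**3. Allow for repeat use.** The repeat-use rates and the ICC below are assumptions.

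Design effect D = 1 + ICC × (Σm²/Σm − 1), where m is the number of dosing instances per woman. The adjusted limit is L at the same proportion with n = Σm / D.

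Example (15% dose twice, 5% three times): 487 women once, 91 twice, 30 three times.
- Σm = 487 + 182 + 90 = 759
- Σm² = 487 + 364 + 270 = 1121, ratio 1.477
- At ICC 0.8, D = 1 + 0.8 × 0.477 = 1.382 and effective n = 759 / 1.382 = 549

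False-pass rates come from at least 40,000 simulated trials per case, beta-binomial within woman, true proportion 90% (simulation error up to about 0.1 point).

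| Assumed pattern | Instances | D, ICC 0.3–0.8 | Lowest pass: planned → adjusted | False-pass, ICC 0.1 | False-pass, ICC 0.3–0.8 |
|---|---|---|---|---|---|
| 5% twice | 638 | 1.028–1.075 | 590 → 590 | about 2.0% | 2.0–2.3% |
| 10% twice | 669 | 1.055–1.146 | 618 → 618–619 | about 2.1% | 2.1–2.8% |
| 10% twice, 5% three times | 729 | 1.124–1.331 | 673 → 674–675 | about 2.1% | 2.4–3.6% |
| 15% twice, 5% three times | 759 | 1.143–1.382 | 700 → 701–703 | about 2.3% | 2.8–4.2% |

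The first row can lie below 2.33% because counts are discrete: at 638 independent instances the rate would be 1.87%.

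**4. Where a verdict can change.** Lower limits at ICC 0.8, planned → adjusted:

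| Pattern | Observed 92.5% | Observed 93% |
|---|---|---|
| 5% twice | 90.17 → 90.08 | 90.74 → 90.64 |
| 10% twice | 90.24 → 90.06 | 90.80 → 90.62 |
| 10% twice, 5% three times | 90.34 → 89.97 | 90.90 → 90.53 |
| 15% twice, 5% three times | 90.39 → 89.97 | 90.95 → 90.54 |

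At 92.5% the verdict flips in the two heavier patterns. At 93% it never does.

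**5. Why these sizes do not carry over to B.** A package holds one tablet (Section 4.3.1), so a woman who fails B must hold at least two packages.
- 5% pattern at a true 90%: 578 single-dosers × 0.10 = 58 failing, plus 30 repeat dosers, gives 88 of 608 (14%) with several packages.
- 15%/5% pattern: 487 × 0.10 = 49, plus 121, gives 170 of 608 (28%).

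Both conflict with Section 4.3.2's expectation of one package for nearly everyone. Two failing B instances in one woman also need at least four tablets, hence two purchase days. The cap of nine allows at most four such instances (4 × 2 = 8; a fifth would need 10). A common ICC model does not describe B.

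**The case against.** The strongest reply is that nothing goes wrong at the repeat use the protocol expects. If 5% of women dose twice, the boundary does not move and the false-pass rate stays below 2.5%. At ICC 0.1 there is no inflation above 2.5% in any of the four patterns, and the protocol gives no reason to prefer a higher value. A good result is also safe: at a true 95% with one dose per woman, the rule passes with probability 0.998. Section 9.3 itself recognises repeat doses and adds a by-subject analysis, and endpoint H and measure K would reveal heavy repeat use. The SAP, which is not shown, could specify the interval further.

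Most of this stands, and it is why the point is minor. It does not remove the flaw. None of those supplementary results governs the 90% decision. Section 4.3.2 also sets the purchase limits so that overuse can be observed, so the interval should hold if overuse occurs.

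Two stronger readings are tempting. One is that both endpoints face a materially inflated error; for B, step 5 of the working shows that the documents do not support this. The other is that a few women using all nine packages could distort A badly. If 12 women (2% of 608) take nine doses on top of the 10%/5% pattern (729 + 12 × 8 = 825 instances), the false-pass rate would be 4.3–8.0% at ICC 0.3–0.8. That needs each of them to buy on at least three days, against the stated expectation that few return. It is a remote bound, not a forecast.

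**Conclusion.** The point holds at low severity. The limit compared with 90% for A and B assumes independence that the design does not guarantee, and the by-subject analysis does not govern the decision.

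For A, with 608 users and the assumed patterns, the pass boundary is 0 instances too low if 5% dose twice, 0–1 if 10% do, and 1–3 if 15% dose twice and 5% three times (ICC 0.3–0.8). The false-pass rate reaches about 4.2% at most in these patterns and stays within 2.5% at ICC 0.1. Only results close to the boundary are affected.

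For B the interval has the same flaw in principle, but no magnitude should be quoted. All sizes rest on repeat-use rates and ICCs that the protocol does not give.

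**What to change.** Keep the dosing-instance proportion and the 90% threshold. State in Section 9.3 that the deciding lower limit for A and B accounts for clustering by subject. One workable form:

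- Use the exact interval with the number of instances divided by a design effect, at the observed proportion.
- Take the design effect as the by-subject robust variance over the binomial variance, without a small-sample factor and floored at 1. Set it to 1 if no woman doses more than once; the interval is then exactly the planned one.
- If there are no failures, use the number of women as the sample size (608 of 608 gives 99.40%). A cluster bootstrap is unsuitable here, because with no or very few failures it returns a limit at or near 100%.
- Keep the by-subject analysis as a sensitivity check.

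In the four patterns above this brings the false-pass rate to about 1.9–2.5%.

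The cost is a short addition to Section 9.3, a few lines of code and a slightly lower limit: at an observed 92.5% and ICC 0.8, 90.17 − 90.08 = 0.09 points if 5% dose twice and 90.24 − 90.06 = 0.18 points if 10% do. Section 9 may require a protocol amendment if this counts as a major change to the primary analysis. The correction is only partial if a few women supply many doses: in the nine-dose case for A, the false-pass rate remains 2.9–4.0%.
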